6.2.2 The research cannot be practically conducted without the waiver

This pragmatic intervention will be implemented across up to 62 facilities over a short time frame. The goal is to develop a scalable system that can be integrated within clinical care. For

both reasons delivery of HIPAA authorization via trained research personnel trained is not practical for the purposes of this research.

6.2.3 The use or disclosure of PHI will carry minimal risks

Given the track record thus far of managing over 100 projects securely through the RADx-UP consortium, the risk for loss of privacy for participating in the RADx-UP survey will be minimized to the greatest extent feasible. Furthermore, the RADx-UP data coordinating center has developed processes for separating identifiable information and anonymizing the remaining data so as to enable wider use while minimizing risks to patient privacy. Finally the RADx-UP Common Data Elements survey is an ‘opt in’ process, thus patients can chose not to participate or provide protected health information as they take the survey.

The risks for participants for the opt out electronic health record data sharing process are low since data shared with Stanford University will not be traceable back to the participant.

7.0 TRIAL IMPLEMENTATION

Below we outline trial implementation according to anticipated chronological timeline.

7.1 Governing Board Review

All dialysis facilities have a CMS mandated governing board responsible for facility-level operations. The governing body typically includes the medical director (nephrologist), facility manager, and members of the nursing or social work teams. This governing body meets monthly to review facility data on census, hospitalizations, regulatory reviews etc. Among the selected facilities, we will review study goals and procedures for the selected facilities. The governing body can request to opt out of the study.

7.2 RADx-UP Survey

Among participating facilities, Research Information Sheet – Trial will be provided to all patients dialyzing at the facility, and to new patients during their admission process to the facility. Patient facing flyers, in English and Spanish, will be posted throughout the facility, advertising the opportunity for participation in the RADx-UP Common Data Elements survey (Appendix C). For patients expressing interest, they will be able to follow a web address on their smart phone or use the facility iPAD to access the survey. The survey will begin with Research Information Sheet – Survey, and among those proceeding, we expect a ~30-minute survey (Appendix X for Common Data Elements Survey). Data from this survey will be stored on Stanford University’s PHI secure servers, accessible to Stanford PIs, analysts and statisticians only. Data will be downloaded, cleaned, and submitted to the NIH RADx-UP Data Coordinating Center (see Section X, Data management)

7.3 Randomization

We will sort US Renal Care facility ID numbers by location and facility size. Within US census region (Northeast, Midwest, South, and West) and facility size strata (< median or >=median size), we will randomly select two facilities per county, oversampling by 30%.

7.4 Intervention: SARS-CoV-2 Testing

Facilities will be randomized to dynamic versus static frequency testing. As standard of care, each patient is individually checked in for each dialysis treatment, with weight and vitals assessment prior to dialysis. On the day of the test, as patients are checking in, facility staff will screen each patient for current health status, as per the current standard routine procedures.

As part of the intervention, each patient will then be offered the anterior nares SARS-CoV-2 test, and his or her response recorded. If the patient agrees to the test, facility staff will use the following PPE surgical face mask, gloves, gown and eye protection. He/she will perform the anterior nares test following CDC guidelines (<https://www.cdc.gov/coronavirus/2019-nCoV/lab/guidelines-clinical-specimens.html>) for anterior nares swab:

Anterior nasal specimen (performed by a healthcare provider or the patient after reviewing and following the collection instructions):

- Insert the entire collection tip of the swab provided (usually $\frac{1}{2}$ to $\frac{3}{4}$ of an inch, or 1 to 1.5 cm) inside the nostril.
- Firmly sample the nasal wall by rotating the swab in a circular path against the nasal wall at least 4 times.
- Take approximately 15 seconds to collect the specimen. Be sure to collect any nasal drainage that may be present on the swab.
- Repeat in the other nostril using the same swab.
- Place swab, tip first, into the transport tube provided.

Staff will then follow standard procedures including labeling and batch shipment to Ascend Clinical Laboratory at the end of the day. The intervention of testing will be offered for a period of three months.

7.5 Testing at Ascend Clinical Laboratory

Patients receiving in-center dialysis have monthly laboratory testing performed, while undergoing dialysis and without requiring needlestick/phlebotomy. The monthly laboratory tests are standard of care and inform dialysis prescription and medication changes (e.g., hemoglobin informing use of erythropoietin stimulating agents). Ascend Clinical Laboratory (<http://clinical.aclab.com/about-us/>) is a fully accredited, CLIA certified laboratory with a throughput of more than 2 million tests per month. Ascend Clinical serves as the contract central laboratory for US Renal Care for these tests, as well as for the symptomatic in-facility anterior nares rtPCR testing that is already in place at US Renal Care. The two partners have established processes for sample collection, shipment and electronic health record communication for release

of health results. Ascend Clinical will ship sample collection kits to selected facilities. US Renal Care staff will follow standard procedures for collection, labeling and shipment back to Ascend Clinical Laboratory. Results will be released into the electronic health record system with an expected time frame of < 48 hours (i.e., prior to the return of the patient to the facility for dialysis).

7.6 Test Results

Standard processes for notification of facilities of ‘critical results’ are already in place, due to the extant clinical partnership between US Renal Care and Ascend Clinical Laboratory. As part of this study, any positive SARS-CoV-2 will be designated as critical results. Critical results require Ascend Clinical Laboratory staff to make at least two attempts to reach a treating RN to inform them of the results. As a failsafe, a project manager hired specifically to work on this project will be informed if RN cannot be reached, and will reach out to both the patient and the treating physician. In addition positive test results are reported to the local Department of Public Health as well. Triage to higher level of care will occur following existing facility protocols and CDC guidelines as necessary.

7.7 Data Collection

In addition to data that patients may choose to provide as part of the RADx-UP Common Data Elements survey, we will track the following data from the electronic health record (PHI is accompanied by asterixis)

Patient Clinical data:

- Age
- Sex
- Self-reported race/ethnicity
- Comorbidities (e.g., diabetes, heart failure, primary cause of ESKD, history of kidney transplant)
- Medications
- Body mass index
- Vaccination status
- Dialysis-related characteristics: vascular access, treatment length, treatment frequency, average ultrafiltration rate; number of years on dialysis
- Patient residence zip code *
- Dates of SARS-CoV-2 screening tests offered and resulted *
- Results of SARS-CoV-2 screening tests *
- Dates of COVID-19 vaccination *
- COVID-19 dates *
- Hospitalizations, dates and admission and discharge diagnosis as applicable*
- Death, dates and cause as applicable*
- Transfer out of facility date as applicable*

Patient laboratory data:

- Albumin
- Hemoglobin
- Sodium
- Potassium
- Phosphorous
- Kt/V_{urea} an index of dialysis efficiency
- Hepatitis B semi quantitative titers
- SARS-CoV-2 S1RBD semi-quantitative IgG, as available

The following facility level data will be collected:

Facility data (US Renal):

- Facility % of patients with hemodialysis catheters as vascular access
- Zip code
- Covered area
- Number of dialysis chairs

7.8 Data Confidentiality Procedures

7.8.1 RADx-UP Common Data Elements Survey

Redcap survey data will be transferred from Stanford University to the RADx-UP Data Coordinating Center (Duke Clinical Research Institute), who will store data in two separate files, one hosting all identifiable information and one with anonymized data. These data will stay in a password-protected secure electronic system and only staff responsible for maintaining the security of data at Stanford University and the RADx-UP DCC will be able to access this information. If applicable these data will be linked with Centers for Medicare and Medicaid Services claims data to enable further research into outcomes. If the participant permits, these data will also be used to contact the participant for future research.

7.8.2 Limited PHI Electronic health record

Each patient at a selected dialysis facility will be assigned a unique (random) research identification number. This ID number will be associated with all participant data that are collected, entered, and analyzed for the study. If a patient is identified by the social workers as unable to participate in opt out consent and/or if he/she selects to opt out of the limited PHI data sharing, he/she will not receive this research ID number. If the opt out selection occurs during the trial, the research ID will be eliminated from future data sharing processes.

The link between participants' names and study ID numbers will be kept in a separate electronic file on secure US Renal Care servers. US Renal Care will ensure that all data prepared for analysis are anonymized, prior to transfer to Stanford University Investigators.

7.9 Data extraction and transfer procedures

For the purposes of this study data will be collected using two methods: a) by RADx-UP survey and b) through limited PHI data extraction from electronic health records.

7.9.1 RADx-UP Survey

Electronic survey data will be rendered remotely from the study sites via the Stanford University School of Medicine REDcap platform, which is a highly secure online survey and database management system. Data will be downloaded from REDcap at regular intervals for analysis onto password protected computers and saved on PHIsafe, HIPAA secure, encrypted Stanford University School of Medicine servers. A log (saved in REDcap) will be maintained to track when, and by whom data are entered as well as downloaded for analysis (including what data are downloaded and for what specific purpose). Only study staff at Stanford University will have download access. Study staff will subsequently clean and upload the data to RADx-UP Data Coordinating Center (Duke Clinical Research Institute) servers.

7.9.2 Limited PHI Data

We will work with US Renal Care health management systems to identify the relevant data fields in the electronic health record (data elements specified under 6.7.). Patients participating in the study will be identified using their research identification number. US Renal Care will collate the selected data fields for each research ID from the electronic health record, and transfer anonymized data to Stanford University using a secure data pipeline set up by Stanford University investigators. Only study staff at Stanford University will have access to the data.

7.10 Statistical Analysis Plan

We will compare the proportion of the total number of times individuals accept performing the test (# of times individuals respond yes / total # of times individuals are asked to perform the test) in the static versus dynamic testing frequency arms. We will use a log-binomial model predicting the probability of acceptability (Y) from intervention arm applying a generalized estimating equation (GEE) approach to take into account the clustering by dialysis facility and the multiple observations per patient. A similar method will be used for estimating the effect of the intervention on the outcome of death or hospitalization. Alternatively, we will use a frailty model which allows for a survival analysis of heterogeneous populations due to the clustering within facilities and multiple observations for each individual(46).

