5.5 Sample Size

We performed power calculations for the primary outcome of test acceptability. Briefly, we followed formulas given by Donner and Klar (2000) for the design of cluster randomized trials comparing probabilities for two groups with an adjustment for the clustered design (Variance

Inflation Factor) by dialysis facility. Assuming a type I error of $\alpha = 0.05$, 80% power ($\beta = 0.2$), a test acceptability proportion equal to 0.4 in the static arm and 0.65 in the dynamic arm – corresponding to a 25% absolute difference, a high degree of correlation between patients within the same facility (Interclass correlation coefficient, ICC=0.5), and that we will be able to recruit ~40 patients per facility (median number of patients per facility at US Renal), we will require 2480 patients from 31 facilities per intervention arm. The assumed ICC reflects the belief that we will observe a high dependence among individuals within a cluster accepting to do the test, i.e., test acceptability is likely related, through the neighborhood composition, for individuals within the facility. With this sample size we will be able to detect a difference of at least 25% for acceptability rates in the static arm ranging from 10% to 60%.

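### The primary model uses intervention arm only; a short pre-specified facility-level baseline adjustment could raise power at little cost

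*Combined protocol and SAP*

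**What the plan says.** Section 7.10 (Statistical Analysis Plan) gives the whole primary model: "We will use a log-binomial model predicting the probability of acceptability (Y) from intervention arm". A GEE handles clustering by facility and repeated offers to the same patient. Section 5.10 repeats that these two features will be accounted for and adds nothing on adjustment. Neither section names a covariate, a stratum, a county-pair term or an adjusted sensitivity analysis.

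Section 5.5 (Sample Size) uses "Interclass correlation coefficient, ICC=0.5" and explains the high value by a belief that "test acceptability is likely related, through the neighborhood composition, for individuals within the facility".

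Section 7.7 (Data Collection) lists "Vaccination status", age, race/ethnicity, comorbidities and residence zip code for each patient, and a few descriptors of each facility. Sections 5.2 and 7.3 select two facilities per county, within strata of census region and facility size.

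**The concern.** The plan names a likely source of its largest variance component, collects data that can stand in for that source, and then leaves those data out of the primary model. With 31 facilities per arm, chance differences in facility composition between the arms feed directly into the standard error of the treatment comparison. The design has almost no reserve above 80% power, and that power is for a large 25-point difference. If the true difference is smaller, precision that could be had from data already collected may decide whether the trial is informative. The covariates must be fixed in advance, because a list chosen after acceptance data are seen would weaken the primary result.

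**Working it through.** **Inputs, all from section 5.5.** "Assuming a type I error of $\alpha = 0.05$, 80% power"; "a test acceptability proportion equal to 0.4 in the static arm and 0.65 in the dynamic arm"; ICC 0.5; "we will be able to recruit ~40 patients per facility"; and "we will require 2480 patients from 31 facilities per intervention arm". Sidedness is not stated, but a two-sided test reproduces the design. Like section 5.5, the working counts one response per patient.

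**Step 1: reproduce the plan's figure.**
- Unclustered n per arm = (1.96 + 0.842)² × [0.4(0.6) + 0.65(0.35)] / 0.25² = 58.7.
- Variance inflation = 1 + 39 × 0.5 = 20.5.
- Facilities per arm = 58.7 × 20.5 / 40 = 30.09, rounded up to 31. Total patients = 2 × 31 × 40 = 2480, as stated.
- Power with 31 facilities (1240 patients) per arm = Φ(0.25 / √(0.4675 × 20.5 / 1240) − 1.96) = 81.2%. With a t reference on 60 df it is 79.9%.

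**Step 2: where the variance lies.** Between-facility share of the variance of an arm's proportion = 0.5 / (0.5 + 0.5/40) = 97.6%.

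**Step 3: effect of facility-level terms.** Let R² be the share of between-facility variance explained. The documents give no value, so a range is assumed. The effective inflation is (1 − 0.5) + 40 × 0.5 × (1 − R²), which replaces 20.5 in the power formula.

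| R² (assumed) | Inflation | Power, normal | Power, t on 60 df |
|---|---|---|---|
| 0% | 20.5 | 81.2% | 79.9% |
| 10% | 18.5 | 84.9% | 83.8% |
| 20% | 16.5 | 88.7% | 87.7% |
| 30% | 14.5 | 92.2% | 91.4% |

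**Step 4: patient-level terms alone.** If half of the within-facility variance is explained and none of the between-facility variance, inflation is 0.5 × 0.5 + 20 = 20.25 and power is 81.6%, a gain of 0.4 points.

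**Step 5: sensitivity to the ICC.** By the same formula, arm-only power is 95.1% at ICC 0.3 and 99.1% at ICC 0.2. Explaining 10% of between-facility variance then adds 1.6 and 0.4 points.

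**Step 6: a smaller true difference.** For 0.40 versus 0.60 at ICC 0.5, arm-only power is 61%. With 25% of between-facility variance explained it is 73%.

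**Step 7: simulation.** Beta-binomial data were generated for 62 facilities of 40 patients, with one facility-level covariate.
- With the covariate explaining about 26% of the variance in facility proportions, power of a log-link Poisson fit with robust variance rose from 76.5% to 87.1%, and power of a facility-level analysis of covariance from 78.8% to 89.4%. Type I error was 4.4% to 5.3%.
- With a useless covariate the two methods went from 76.2% to 76.1% and from 79.5% to 78.4%, a cost of about 0 to 1 point.
- In the 26% setting, fitted probabilities exceeded 1 in 91% of runs, a sign that a log-binomial fit with covariates may fail.

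**The case against.** The strongest reply is that nothing is wrong. An arm-only GEE is a valid analysis of a randomized comparison, and it matches the unadjusted calculation in section 5.5, which targeted 80% by choice. This stands. A reader might infer that the primary analysis is biased, invalid or underpowered for its stated difference; the documents support none of these.

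Second, every gain above zero rests on an assumed R². This also stands. A reader might infer that the ICC is wholly due to composition and that adjustment would recover most of it. Section 5.5 states only a belief about neighborhood composition, and sections 5.9 and 5.11 describe other possible facility-level influences, such as encouragement by staff and nephrologists, adherence feedback and workflow.

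Third, section 5.2 expects county-based selection to balance socio-demographics. That may leave less for covariates to explain, and the relevant R² is then what they add beyond county, region and size. But neither section 5.2 nor section 7.3 says that one facility of each county pair goes to each arm, and an arm-only model with facilities as independent clusters does not credit such balance in the standard error.

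Fourth, patient covariates gain little when facilities dominate the variance. Step 4 confirms this. It is a reason to adjust at facility level, not a reason to leave the model unadjusted.

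**Conclusion.** The point holds as an efficiency gap that is worth closing. The primary model omits both the factors used to select facilities and the baseline data that could describe facility composition. At the planned ICC of 0.5, the gain over arm-only power of about 81% would be roughly 4, 8 or 11 points if the added terms explain 10%, 20% or 30% of between-facility variance; powers are about 1 point lower on the t scale. These shares are assumptions, and the true gain cannot be derived from the documents. It could be close to zero if the chosen terms are uninformative, if county, region and size already capture composition, or if the ICC is well below 0.5. It comes from facility-level terms and hardly at all from explaining differences between patients within a facility.

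**What to change.** In section 7.10, pre-specify a primary model with:
- intervention arm;
- the region and facility-size strata, and the county pair if allocation is within pairs;
- a short list of facility-level baseline covariates, computed from patients on the census when the intervention starts, for example proportion vaccinated, race/ethnicity composition and mean age.

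Patient-level terms are optional. Use baseline values only: on-study test results, COVID-19 dates and later vaccination should not enter. Fixing facility values on the starting census also settles what applies to patients who begin dialysis there during the trial.

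Fit a log-link Poisson GEE with robust variance and a small-sample correction for 62 clusters. Report the standardized risk ratio and absolute difference, and keep the arm-only model as a sensitivity analysis.

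The cost is SAP wording and the derivation of a few facility summaries from fields already to be extracted. Statistically, it is a few degrees of freedom: with t on 50 df instead of 60 and nothing explained, power falls from 79.9% to 79.6%, and the simulated loss was about 0 to 1 point. County pairs are the exception. If the 62 facilities form 31 pairs, pair indicators would use 30 degrees of freedom, so the SAP should first state how pairs are allocated and then how they enter the model.

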5.10 Outcomes

The primary outcome is test acceptability, i.e., the proportion of tests accepted from the total number of tests offered. Statistical analyses will account for multiple observations per patient and clustering by dialysis facility.

Secondary outcomes include time to death or hospitalization. Patients on dialysis experience the highest rates of hospitalization across all CMS at-risk beneficiaries' group(9), and among the highest death rates of patients hospitalized with COVID-19. We posit that by early identification of infected persons and by reducing transmission of SARS-CoV-2 we will reduce overall hospitalizations and death among patients receiving dialysis. Hospitalizations and deaths can be ascertained from dialysis facility records since they are mandated for tracking at monthly Quality Assessment and Performance Improvement Meetings. Thus we will use the US Renal Care electronic health record to ascertain dates, and admission and discharge diagnoses for hospitalizations. We will use the electronic health record to track dates and cause of death as applicable.

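### The death-or-hospitalization comparison names no covariate besides arm and requests no pre-trial facility hospitalization rates, giving up precision of unknown size on an outcome with no stated power

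*Combined protocol and SAP*

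**What the plan says.** Section 7.10 is the whole analysis plan. Acceptability is modelled by a log-binomial GEE with intervention arm as the only predictor mentioned, allowing for clustering by facility and repeated offers. For the clinical outcomes it adds: "A similar method will be used for estimating the effect of the intervention on the outcome of death or hospitalization". A frailty model is the stated alternative. No covariate is named for either.

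Section 7.7 lists four facility-level items: catheter percentage, zip code, covered area and number of chairs. Patient-level hospitalization dates are also listed, but with no look-back period before the trial.

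The information exists. Section 5.10 says hospitalizations and deaths are "mandated for tracking at monthly Quality Assessment and Performance Improvement Meetings". Section 7.1 says of each facility: "This governing body meets monthly to review facility data on census, hospitalizations, regulatory reviews etc". So both the count and its denominator are on hand.

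The power statement in section 5.5 concerns test acceptability only. It gives no event rate, effect size, intracluster correlation or power for death or hospitalization.

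**The concern.** Objective 3.2 is the clinical-effectiveness question, and it is answered by comparing up to 31 facilities with 31. Facilities may differ in case mix and admission practice in ways that persist over time. Where they do, a facility's own recent hospitalization rate predicts its rate during the trial, and adjusting for it removes part of the between-facility noise. GEE and frailty terms make the standard error honest about that noise, but they do not explain any of it.

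At stake is the width of the confidence interval on a secondary result. Prespecification also matters: a covariate chosen after the outcomes are seen carries less weight than one fixed in advance.

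**Working it through.** **1. The plan's own figure.** Section 5.5 assumes "a test acceptability proportion equal to 0.4 in the static arm and 0.65 in the dynamic arm", an "Interclass correlation coefficient, ICC=0.5" and about "40 patients per facility", with type I error 0.05 and power 80%. Two-sided, with unpooled variance:

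- n per arm before clustering = (1.960 + 0.842)² × (0.4×0.6 + 0.65×0.35) / 0.25² = 58.7
- Variance inflation = 1 + 39 × 0.5 = 20.5
- 58.7 × 20.5 = 1203.5 patients per arm; / 40 = 30.1, rounded up to 31 facilities
- 31 × 40 × 2 = 2480

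This reproduces "we will require 2480 patients from 31 facilities per intervention arm", with 2480 as the two-arm total. The calculation is sound for acceptability and does not extend to the clinical outcomes.

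**2. Gain from adjustment, admission rates.** From the documents: 40 patients per facility, and 4 months of follow-up (3 months of intervention plus up to 1 month, section 3.2). Assumed, because the documents give none of these: 1.5 admissions per patient-year; between-facility coefficient of variation CV = 0.3; a 12-month look-back; dispersion φ = 1 (Poisson) or 2 (within-facility variance doubled); correlation ρ between a facility's true rates in the two periods.

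- Expected admissions per facility: trial 40 × 1.5 / 3 = 20; look-back 40 × 1.5 = 60
- Variance of the observed log rate = φ/events + CV²
- φ = 1: trial 0.050 + 0.090 = 0.140; look-back 0.0167 + 0.090 = 0.1067
- φ = 2: trial 0.100 + 0.090 = 0.190; look-back 0.0333 + 0.090 = 0.1233
- R² = (ρ × CV²)² / (V_trial × V_pre), and the SE ratio is √(1 − R²)
- Equivalent number of facilities = 62 / (1 − R²)

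| ρ | R², φ=1 | SE falls | R², φ=2 | SE falls | Equivalent facilities |
|---|---|---|---|---|---|
| 0.3 | 0.049 | 2.5% | 0.031 | 1.6% | 64–65 |
| 0.5 | 0.136 | 7.0% | 0.086 | 4.4% | 68–72 |
| 0.8 | 0.347 | 19% | 0.221 | 12% | 80–95 |

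**3. First-event endpoint.** Section 5.10 specifies time to death or hospitalization, not a recurrent admission rate. Simulating any admission within 4 months under the same assumptions (φ = 1, ρ = 0.8) gives R² of about 0.30 rather than 0.35, so the SE falls about 16% rather than 19%.

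**4. Cross-check by intracluster correlation.** Assume a 20% static-arm risk of death or hospitalization, a baseline of 120 patient-equivalents per facility and a between-period correlation of facility effects of 0.8. The correlation between observed facility means is r = 0.8·ICC / √[(ICC + (1−ICC)/40)(ICC + (1−ICC)/120)], and variance falls by r².

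| Outcome ICC | Variance falls | Detectable relative reduction (80% power), unadjusted → adjusted |
|---|---|---|
| 0.005 | 4% | 23.4% → 23.0% |
| 0.01 | 10% | 25.1% → 23.9% |
| 0.05 | 37% | 35.6% → 28.7% |
| 0.10 | 49% | 44.8% → 33.2% |

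**5. Deaths.** Assume 10–20% yearly mortality. A facility of 40 then has 4–8 look-back deaths and 1.3–2.7 trial deaths. With ρ = 0.8, φ = 1 and CV 0.2–0.4, step 2 gives R² of 0.004–0.11 and an SE reduction of 0.2–5.5%. At 15% mortality and CV 0.3 the SE falls 1.7%.

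**The case against.** The strongest reply is that the plan has made no error. Several parts of it stand.

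- **Silence is not exclusion.** A reader might infer that the plan commits to an arm-only model for the clinical outcomes. It does not. The sentence in 7.10 may refer only to the GEE approach, and section 7.7 collects age, comorbidities and vaccination without saying how they will be used. The gap is one of prespecification.
- **There is no bias.** A reader might infer that a chance difference between arms in pre-trial rates would distort the result. Randomization keeps the unadjusted estimate unbiased, and the cluster-adjusted standard error covers chance imbalance.
- **The between-period correlation decides the size.** Section 5.7 expects community transmission to change during the trial, and a look-back through the pandemic may mix different local waves. A correlation of 0.8 cannot be taken for granted.
- **The design helps somewhat.** Facilities are drawn two per county (5.2) within region and size strata (7.3), which may already balance some between-facility variation. However, 7.10 does not carry county or stratum into the model, and facilities may opt out (5.3), which can break pairs.
- **The extract is not identical to the trial population.** Section 5.4 asks for an established facility but guarantees no length of history. Aggregate counts would also include patients removed from the patient-level data under 6.1.1 and 7.8.2. This weakens the covariate slightly. It does not invalidate it, since it is measured before the intervention in both arms.

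None of this removes the point that usable baseline information exists and is not requested.

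**Conclusion.** The point holds as a missed, inexpensive gain in precision on a secondary comparison of death or hospitalization. It does not affect the validity of the trial or the primary outcome.

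Its size cannot be derived from the documents. The range in the working runs from negligible to useful, depending mainly on how stable facility rates are and how large the outcome ICC is. It would be tempting to say that adjustment is worth 18 to 33 extra facilities (80–95 against 62), but that rests on a between-period correlation of 0.8, which the documents do not support. At 0.5 it is about 6 to 10.

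It would also be tempting to extend the argument to a pre-trial death rate. At facilities of about 40 patients the gain is close to nil, and a log death rate is undefined where no deaths occurred.

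**What to change.** - **Section 7.7:** add aggregate monthly census and hospitalization counts for each facility over a defined pre-trial look-back, for example up to 12 months, or as many months as the facility has.
- **Section 7.10:** prespecify the facility's log pre-trial hospitalization rate as a covariate in the hospitalization model and in the combined death-or-hospitalization model, whether GEE or frailty, and report the unadjusted result alongside. Do not add a pre-trial death rate.

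The cost is one small aggregate extract per facility and one model degree of freedom among up to 62 facilities. The extract needs no patient-level data, but its counts will include patients who opt out of the patient-level dataset, and the plan should say so.
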